7.1.2. Packaging and Labelling

The investigational products will be supplied by the sponsor or its designee in accordance with current Good Manufacturing Practices (cGMP).

Clinical trial materials will be labeled according to the country's regulatory requirements. All investigational products will be stored, inventoried, reconciled, and destroyed according to applicable regulations.

Ixekizumab and placebo to match will be supplied as injectable solutions in 1-mL, single-dose, prefilled, disposable manual syringes with study-specific labels. Each syringe of ixekizumab is designed to deliver ixekizumab 80 mg. The syringes (and contents) containing either

ixekizumab or placebo will be visibly indistinguishable from each other. Syringes will be supplied in cartons, with the appropriate quantity of syringes specific to the planned dispensing schedule of the investigational product.

7.2. Method of Treatment Assignment

Patients who meet all criteria for enrollment will be randomized to double-blind treatment at Week 0 (Visit 2). Assignment to treatment groups will be determined by a computer-generated random sequence using an interactive web-response system (IWRS). The IWRS will be used to assign double-blind investigational product to each patient. Site personnel will confirm that they have located the correct assigned investigational product package by entering a confirmation number found on the package into the IWRS.

To achieve between-group comparability, the randomization will be stratified by baseline CRP (non-elevated or elevated) and TNF inhibitor experienced or naïve. The study will enroll approximately 60% of patients with baseline CRP elevated (>5.00 mg/L) and approximately 40% of patients with non-elevated baseline CRP. At least 61 bDMARD-naïve patients will be enrolled per arm.

Once a specific stratum is fully enrolled, the sponsor may stop further enrollment of patients fitting the criteria of that stratum.

7.2.1. Selection and Timing of Doses

Investigational product is to be administered at approximately the same time each day, as much as possible. For injections not administered on the scheduled day of the week from Weeks 0 to 16, the missed dose is to be administered within 3 days of the scheduled day; after Week 16, the missed dose is to be administered within 5 days of the scheduled day. Dates of subsequent study visits are not to be modified according to this delay.

A paper Study Drug Administration Log will be completed by randomized patients for each injection throughout study participation. The data from the Study Drug Administration Log must be transcribed into the electronic case report form (eCRF) by site personnel.

Patients will be instructed to contact their study site in the event of an injection problem. In addition, site personnel review all Study Drug Administration Logs at each visit to identify any product complaints, and they will complete a Product Complaint Form for each operation failure reported on a Study Drug Administration Log (see Section 9.2.3 for additional instructions regarding complaint handling).

7.3. Blinding

This is a double-blind study.

Initial randomization (study treatment administered between Weeks 0 and 16) will remain blinded to study site personnel and patients until the final clinical trial database lock has occurred.

Randomization will be blinded to sponsor until the clinical trial database through Week 16 has locked

Emergency unblinding for AEs may be performed through the IWRS, which may supplement or take the place of emergency codes generated by a computer drug-labeling system. This option may be used ONLY if the patient's well-being requires knowledge of the patient's treatment assignment. All actions resulting in an unblinding event are recorded and reported by the IWRS.

If an investigator, site personnel performing assessments, or patient is unblinded, the patient is to be discontinued from the study treatment. In cases where there are ethical reasons to have the patient remain on study treatment, the investigator must obtain specific approval from a Lilly clinical research physician or Lilly clinical research scientist for the patient to continue on study treatment.

In case of an emergency, the investigator has the sole responsibility for determining if unblinding of a patient's treatment assignment is warranted for medical management of the event. The safety must always be the first consideration in making such a determination. If a patient's treatment assignment is unblinded, Lilly must be notified immediately. If the investigator decides that unblinding is warranted, it is the responsibility of the investigator to promptly document the decision and rationale and notify Lilly as soon as possible.

7.4. Dosage Modification

No investigational product dose modifications are permitted (refer to Section 9.4.10.2.1 for instances where drug may be withheld).

7.5. Preparation/Handling/Storage/Accountability

Investigational products will be supplied by Lilly or its representative, in accordance with cGMP, and will be supplied with lot numbers, expiry dates, and certificates of analysis, as applicable.

The investigational product is to be stored at 2°C to 8°C (36°F to 46°F) in its original carton to protect from light. Investigational product must not be frozen or shaken. Sites will be required to monitor temperature of the on-site storage conditions of the investigational product.

7.6. Treatment Compliance

Patient compliance with study medication will be assessed at each visit. Compliance will be assessed by review of the Study Drug Administration Log, return of empty or unused investigational product packaging, and/or direct questioning. Deviation(s) from the prescribed dosage regimen are to be recorded in the eCRF.

Compliance is defined in Section 10.3.6.4.

7.7. Concomitant Therapy

All concomitant medication taken during the study must be recorded in the eCRF. Patients will maintain their usual medication regimen throughout the study unless specifically excluded in the

protocol. Patients taking permitted medications are to be on stable doses at the baseline visit (Week 0; Visit 2) through Week 16 as specified in inclusion/exclusion criteria (Sections 6.1 and 6.2). Up to Week 16, patients should not start new medications or make any changes to concomitant medications unless changes need to be made for an AE or for safety reasons. Beyond Week 16, some flexibility is allowed in concomitant medication as outlined below.

Additional drugs are to be avoided during the study unless required to treat an AE or for the treatment of an ongoing medical problem. If the need for concomitant medication arises, the investigator is to base decisions on the patient and relevant clinical factors. Any additional medication, whether prescription or over-the-counter, used at baseline (Week 0, Visit 2) and/or during the course of the study must be documented with the start and stop dates in the eCRF. Other medications may be allowed, if approved by the sponsor or its designee.

Only for patients who discontinued study treatment and have entered the Post-Treatment Follow-Up Period (Period 4), AS therapy with another agent previously excluded during the treatment period of the study may be allowed, as determined appropriate by the investigator and approved by Lilly medical.

Patients requiring surgery at any time during the study are to interrupt administration of the investigational product beginning 8 weeks prior to the surgery, or as early as possible within 8 weeks of surgery, and resume administration of the investigational product only after complete wound healing.

Vaccines:

Live vaccines are not allowed during any of the study periods. Use of nonlive seasonal vaccinations and/or emergency vaccination (such as rabies or tetanus vaccinations) is allowed.

NSAIDs and Analgesics:

Blinded Treatment Dosing Period (Period 2):

Nonsteroidal anti-inflammatory drugs, including COX-2 inhibitors, will be allowed up to the maximum recommended doses for pain. Patients must be on a stable dose of NSAIDs/Cox-2 inhibitors for at least 2 weeks prior to baseline randomization. Introduction of a new NSAID or dose adjustment to an existing NSAID is not permitted, unless required for safety reasons.

Short-acting analgesics with no anti-inflammatory action (such as paracetamol) are permitted and may be administered ad hoc as needed and are to be withheld within the 24-hour period prior to any assessment. Aspirin (dose not exceeding 350 mg/day) may be taken to manage cardiovascular risk.

Opiate analgesic use is allowed but not to exceed >30 mg/day of morphine or its equivalent. Patients are to be on stable dose during Period 2. Introduction of a new opiate analgesic or dose adjustment to an existing opiate analgesic is not permitted, unless required for safety reasons or as premedication for MRIs.

Extended Treatment and Post-Treatment Follow-Up Periods (Periods 3 and 4):

After completion of the Week 16 assessments, alterations of NSAIDs, including COX-2 inhibitors (dose change, introduction, or withdrawal) are allowed. Doses are recommended to be stable in the 2 weeks prior to an arthritis assessment.

Short-acting analgesics with no anti-inflammatory action (such as paracetamol) are permitted and may be administered ad hoc as needed but are to be withheld within the 24-hour period prior to any assessment. Aspirin (dose not exceeding 350 mg/day) may be taken to manage cardiovascular risk.

Use of variable doses of opiate analgesics is allowed, but not to exceed an average daily dose of 30 mg morphine or its equivalent.

Conventional DMARDs:Blinded Treatment Dosing Period (Period 2):

Discontinuation of excluded oral or injectable cDMARDs before study enrollment must occur at least 4 weeks prior to baseline. Methotrexate (oral or parenteral up to 25 mg/week), sulfasalazine (up to 3 g/day), or hydroxychloroquine (up to 400 mg/day) may be allowed IF at stable dose for at least 4 weeks prior to baseline randomization.

During Period 2, alteration of cDMARD dose or route, and/or introduction of a new cDMARD are not permitted, unless required for safety reasons. Conventional DMARDs can only be used as single agents and not in combination with other cDMARDs. If, at any time, the investigator believes that side effects or laboratory abnormalities may be attributable to the cDMARD, the cDMARD dose is to be lowered or the medication stopped.

Extended Treatment and Post-Treatment Follow-Up Periods (Periods 3 and 4):

During Periods 3 and 4, adjustment of allowed cDMARDs (for example, dose change, introduction, withdrawal of cDMARDs, or replacement of a current cDMARD with the introduction of a new cDMARD) is allowed after all assessments at Week 16 are completed. Not more than 1 adjustment of cDMARDs at 1 time within 12 weeks is recommended. Conventional DMARDs can only be used as single agents and not in combination with other cDMARDs. Any changes must be recorded in the eCRF.

For all study periods, the maximum allowed doses are 25 mg/week MTX, 400 mg/day hydroxychloroquine and 3 g/day sulfasalazine. Local standards of care are to be followed for concomitant administration of folic or folinic acid if MTX is taken, and for administration of other cDMARDs.

Corticosteroids:Blinded Treatment Dosing Period (Period 2):

Oral corticosteroids: If on oral corticosteroids, the dose must not exceed 10 mg/day of prednisone or its equivalent and must be stable for at least 4 weeks prior to baseline randomization. During Period 2, treatment alterations in oral corticosteroid dose are strongly discouraged.

Parenteral corticosteroids (IV, intramuscular, intra-articular): Treatment with any parenteral corticosteroids is not permitted within 6 weeks prior to baseline or during Period 2.

Inhaled and topical steroids: Regular use of inhaled or topical steroids will be permitted during any study period.

Extended Treatment and Post-Treatment Follow-Up Periods (Periods 3 and 4):

Oral corticosteroids: As of Week 16, adjustments of oral corticosteroids are allowed, however the maximum dose is not to exceed 10 mg/day of prednisone or its equivalent at any time during these periods.

Parenteral corticosteroids (IV, intramuscular, intra-articular): As of Week 16, intra-articular injection of corticosteroid may be allowed, as needed. The joint injected must be designated along with the medication in the eCRF.

Inhaled and topical steroids: Regular use of inhaled or topical steroids will be permitted during any study period.

Other Concomitant Medications (Periods 2, 3, and 4):

Patients requiring surgery at any time during the study are to interrupt administration of the investigational product beginning 8 weeks prior to the surgery, or as early as possible within 8 weeks of surgery, and resume administration of the investigational product only after complete wound healing.

Additional drugs are to be avoided during the study unless required to treat an AE or for the treatment of an ongoing medical problem. If the need for concomitant medication arises, the investigator is to base decisions on the patient and on clinical factors. Any additional medication, whether prescription or over-the-counter, used at baseline (Week 0, Visit 2) and/or during the course of the study, must be documented with the start and stop dates in the eCRF.

Additional systemic drugs are to be avoided during the study, unless required to treat an AE. Other medications may be allowed, if approved by the sponsor or its designee.

Only for patients who discontinued study treatment and have entered the Post-Treatment Follow-Up Period, axSpA therapy with another agent previously excluded during the treatment period of the study may be allowed, as determined appropriate by the investigator and approved by Lilly medical.

Any changes in medications not addressed above are to be discussed with the investigator. Patients must be instructed to consult the investigator or other appropriate study personnel at the site before taking any new medications or supplements.

7.7.1. Continued Access

Investigational product will not be made available to patients after conclusion of this study.

7.7.2. Special Treatment Considerations

Patients will be screened for eligibility in the study as described in Sections 6.1 and 6.2 and will be informed of the study-specific restrictions and requirements of the study. Patients who are not willing to comply with the study restrictions and requirements of the study will not be eligible for enrollment.

All biological agents carry the risk of systemic allergic/hypersensitivity reactions (See Section 9.2.2.1).

Sometimes these reactions can be life threatening. Proteins may also cause redness, itching, swelling, or pain locally at the injection site; therefore, all patients should be closely monitored for signs or symptoms that could result from such reactions, educated on the signs or symptoms of these types of reactions, and instructed to contact the study site immediately if any of these symptoms are experienced following an injection. If a patient experiences an acute allergic/hypersensitivity reaction after an injection of investigational product, he or she is to be managed appropriately and given instruction to receive relevant supportive care. Additionally, for an event judged by the investigator to be a potential systemic allergic/hypersensitivity reaction, a blood sample is to be drawn to test for anti-drug antibody (ADA) as soon as possible (see Section 9.4.4).

For patients who experience a potential allergic/hypersensitivity reaction, consideration for any premedication for future injections will be agreed upon between the investigator and sponsor. Examples of potential allergic/hypersensitivity reactions that might merit premedication include mild-to-moderate skin rashes, mild-to-moderate generalized pruritus and/or urticaria, and mild-to-moderate injection site reactions (for example, injection site erythema, injection site pruritus, and so on). Patients who develop clinically significant systemic allergic/hypersensitivity reactions following administration of investigational product that do not respond to symptomatic medication or result in clinical sequelae (for example, hospitalization) are to be discontinued from study treatment and not receive further doses of investigational product, with or without premedication (see Section 8.1). Medications considered appropriate for premedication include, but are not restricted to, acetaminophen/paracetamol up to 1000 mg and antihistamines (for example, oral diphenhydramine 50 mg) given after all efficacy assessments have been completed for a given visit, and 30 to 60 minutes prior to investigational product SC injections for visits where injections are administered at the clinic. For all other injections, patients may self-premedicate at home prior to administration of investigational product, as directed by the investigator. All such premedications will be recorded as concomitant medications. Corticosteroids are not permitted as agents for premedication.

8. Discontinuation Criteria

8.1. Discontinuation from Study Treatment

The reason for and date of discontinuation from study treatment (investigational product) and reason for and date of discontinuation from study participation will be collected for all randomized patients.

8.1.1. *Permanent Discontinuation from Study Treatment*

For any patient permanently discontinuing from study treatment, the investigational product will be withheld, and the patient will complete the ETV and the Post-treatment Follow-up Period (Period 4), as shown in the Schedule of Activities (Section 2).

The following criteria must be followed for discontinuation from study treatment.

- **Subject Decision**
 - the patient or the patient's designee, for example, parents or legal guardian requests to discontinue investigational product.
- **Discontinuation due to a hepatic event or liver test abnormality.** Patients who are discontinued from investigational product due to a hepatic event or liver test abnormality should have additional hepatic safety data collected via electronic data entry.

Discontinuation of the investigational product for abnormal liver tests should be considered by the investigator when a patient meets one of the following conditions, after consultation with the Lilly designated medical monitor:

- alanine aminotransferase (ALT) or aspartate aminotransferase (AST) >8X upper limit of normal (ULN)
 - ALT or AST >5X ULN for more than 2 weeks
 - ALT or AST >3X ULN and total bilirubin (TBL) level >2xULN or international normalized ratio (INR) >1.5
 - ALT or AST >3X ULN with the appearance of fatigue, nausea, vomiting, right upper-quadrant pain or tenderness, fever, rash, and/or eosinophilia (>5%)
 - alkaline phosphatase (ALP) >3X ULN
 - ALP >2.5X ULN and TBL >2X ULN
 - ALP >2.5X ULN with the appearance of fatigue, nausea, vomiting, right upper quadrant pain or tenderness, fever, rash, and/or eosinophilia (>5%)
- Other laboratory tests

- Neutrophil (segmented) counts (see safety monitoring for neutropenia in Section 9.4.10.2):
 - <500 cells/ μL ($<0.50 \times 10^3/\mu\text{L}$ or <0.50 GI/L)
 - ≥ 500 and <1000 cells/ μL ($\geq 0.50 \times 10^3/\mu\text{L}$ and $<1.00 \times 10^3/\mu\text{L}$ or ≥ 0.50 GI/L and <1.00 GI/L) (based on 2 test results; the second test performed within 1 week from knowledge of the initial result)
 - ≥ 1000 and <1500 cells/ μL ($\geq 1.00 \times 10^3/\mu\text{L}$ and $<1.50 \times 10^3/\mu\text{L}$ or ≥ 1.00 GI/L and <1.50 GI/L) (based on 3 test results as specified in Section 9.4.10.2.1)
 - AND - a concurrent infection
- Total WBC count <2000 cells/ μL ($<2.00 \times 10^3/\mu\text{L}$ or <2.00 GI/L)
- Lymphocyte count <500 cells/ μL ($<0.50 \times 10^3/\mu\text{L}$ or <0.50 GI/L)
- Platelet count $<50,000$ cells/ μL ($<50 \times 10^3/\mu\text{L}$ or <50 GI/L)
- The patient experiences a severe AE, an SAE, or a clinically significant change in a laboratory value that, in the opinion of the investigator, merits the discontinuation of the investigational product and appropriate measures being taken. In this case, Lilly or its designee is to be notified immediately. Refer to Section 9.1.4.
- The investigator, after consultation with the sponsor-designated medical monitor, determines that a clinically significant hypersensitivity reaction has occurred. A clinically significant systemic hypersensitivity reaction is one that occurs after administration of the investigational intervention (for example, drug-related symptomatic bronchospasm, allergy-related edema/angioedema, or hypertension) and requires parenteral medication, does not respond to symptomatic medication, results in clinical sequelae, or in an anaphylactic reaction.
- The patient becomes pregnant.
- The patient develops a malignancy.

Note: Patients may be allowed to continue if they develop no more than 2 nonmelanoma skin cancers during the study.
- Enrollment in any other clinical trial involving an investigational product or enrollment in any other type of medical research judged not to be scientifically or medically compatible with this study.

- The patient, at any time during the study, scores a 3 for Item 12 (Thoughts of Death or Suicide) on the QIDS-SR16

-OR-

develops active suicidal ideation with some intent to act with or without a specific plan (yes to question 4 or 5 on the “Suicidal Ideation” portion of the Columbia–Suicide Severity Rating Scale [C-SSRS])

-OR-

develops suicide-related behaviors as recorded on the C-SSRS.

It is recommended that the subject be assessed by a psychiatrist or appropriately trained professional to assist in deciding whether the subject is to be discontinued from the study.

- The investigator or attending physician decides that the patient is to be withdrawn from study treatment.
- Lilly or its designee stops the patient’s participation in the study or Lilly stops the study for medical, safety, regulatory, or other reasons consistent with applicable laws, regulations, and good clinical practice (GCP).
- The patient becomes HBV DNA positive, at which time the patient is to be referred to a specialist physician. Discussion of the timing of discontinuation from the study and from study treatment is provided in Section 9.4.10.2.2.

Patients discontinuing from the investigational product prematurely for any reason should complete adverse event and other follow-up procedures per Section 2 (Schedule of Activities), Section 9.2 (Adverse Events), and Section 9.4 (Safety) of this protocol.

8.1.2. Discontinuation of Inadvertently Enrolled Patients

If the sponsor or investigator identify a patient who did not meet enrollment criteria and was inadvertently enrolled, then the patient should be discontinued from study treatment unless there are extenuating circumstances that make it medically necessary for the patient to continue on study treatment. If the investigator and the sponsor CRP agree it is medically appropriate to continue, the investigator must obtain documented approval from the sponsor CRP to allow the inadvertently enrolled patient to continue in the study with or without treatment with investigational product. Safety follow up is as outlined in Section 2 (Schedule of Activities), Section 9.2 (Adverse Events), and Section 9.4 (Safety) of the protocol.

8.2. Discontinuation from the Study

Patients will be discontinued in the following circumstances:

- enrollment in any other clinical study involving an investigational product or enrollment in any other type of medical research judged not to be scientifically or medically compatible with this study
- participation in the study needs to be stopped for medical, safety, regulatory, or other reasons consistent with applicable laws, regulations, and good clinical practice (GCP)
- investigator decision
 - The investigator decides that the patient should be discontinued from the study
 - If the patient, for any reason, requires treatment with another therapeutic agent that has been demonstrated to be effective for treatment of the study indication, discontinuation from the study occurs prior to introduction of the new agent
- patient decision
 - the patient or the patient's designee, for example, parents or legal guardian requests to be withdrawn from the study

Patients discontinuing from the study prematurely for any reason should complete adverse event and other safety follow-up per Section 2 (Schedule of Activities), Section 9.2 (Adverse Events), and Section 9.4 (Safety) of this protocol.

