complex, human leukocyte antigen (HLA)-B27. Up to 90% to 95% of patients with r-axSpA are positive for HLA-B27, and the risk of this disease developing is as high as about 5% in HLA-B27-positive individuals and substantially higher in HLA-B27-positive relatives of patients (Braun and Sieper 2007). Most of the other known genetic susceptibility comes from genes involved in cytokine production, specifically including genes in the T helper (Th)17 pathway (Maksymowych 2010; Reveille 2011).

Current standard of care for r-axSpA includes regular exercise, physical therapy, nonsteroidal anti-inflammatory drugs (NSAIDs), and TNF alpha inhibitors (Braun et al. 2011; Ward et al. 2015). Corticosteroid injections may also be of some benefit. Though NSAIDs are the first line of drug treatment for axSpA, they are not effective or well tolerated in all patients (Braun and Sieper 2009). In contrast to patients with RA, patients with axSpA do not respond well to conventional disease-modifying antirheumatic drugs (cDMARDs) including methotrexate (MTX) or systemic corticosteroids (Braun and Sieper 2009; Haibel and Specker 2009).

TNF inhibitors are effective and frequently prescribed when NSAID treatment has failed or cannot be tolerated (Zochling et al. 2006). While TNF inhibitors have proven to be effective treatments for axSpA, an unmet need remains, as not all patients respond well to or tolerate TNF inhibitor treatments (van der Heijde et al. 2006; Heiberg et al. 2008; Inman et al. 2008; Glinborg et al. 2010). While TNF inhibitors have demonstrated significant impact on signs and symptoms, function, and quality of life, they have not been able to demonstrate significant effect on structural progression in prospective clinical studies. The use of these biologic therapies in various diseases also is associated with safety concerns, such as opportunistic infections, demyelinating disorders, blood dyscrasias, reactivation of tuberculosis (TB), and exacerbation of congestive heart failure (Moreland 2005; Smith et al. 2009). There remains, therefore, a significant unmet need for safer, more effective treatments for patients with axSpA (Dougados and Baeten 2011). Ixekizumab may offer an alternative treatment approach to TNF inhibitor therapy in patients with axSpA.

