Investigators are not obligated to actively seek AEs or SAEs in subjects once they have discontinued and/or completed the study (the patient disposition CRF has been completed). However, if the investigator learns of any SAE, including a death, at any time after a subject has been discharged from the study, and he/she considers the event reasonably possibly related to the study treatment or study participation, the investigator must promptly notify Lilly.

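### Protocol 8.2 and 7.7 conflict on patients who start another effective axSpA therapy in Period 4, so their recorded disposition depends on which rule is applied and Period 4 safety tables cannot show which events followed the new agent

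*Protocol*

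**What the plan says.** Protocol 8.2 lists the circumstances in which a patient is discontinued from the study. One is that the patient, whatever the reason, "requires treatment with another therapeutic agent that has been demonstrated to be effective for treatment of the study indication"; in that case "discontinuation from the study occurs prior to introduction of the new agent". The section closes by asking everyone who leaves the study early to complete adverse event and other safety follow-up under Section 2, Section 9.2 and Section 9.4.

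Protocol 7.7 addresses patients who have stopped study treatment and are in the Post-Treatment Follow-Up Period: "AS therapy with another agent previously excluded during the treatment period of the study may be allowed, as determined appropriate by the investigator", subject also to approval by the sponsor's medical staff. It repeats the permission under other concomitant medications: "axSpA therapy with another agent previously excluded during the treatment period of the study may be allowed". For Periods 3 and 4 it also states that, after the Week 16 assessments, "alterations of NSAIDs, including COX-2 inhibitors (dose change, introduction, or withdrawal) are allowed".

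On follow-up, footnote w of the Schedule of Activities requires Visits 801 and 802, at 4 and 12 weeks after the last visit, for treated patients who stop early and for those who complete Week 52. Footnote c of the study design figure makes both visits mandatory for all. Protocol 9.2.1 adds: "Investigators are not obligated to actively seek AEs or SAEs in subjects once they have discontinued and/or completed the study", and ties this to completion of the patient disposition form.

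SAP 6.5 tabulates completion and discontinuation of Period 4, with primary reason. SAP 6.1.5 and Table RHCH.6.2 group Period 4 patients by the regimen they received before entering it.

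**The concern.** A patient who starts, say, a TNF inhibitor during Period 4 is covered by two instructions. Under 8.2 that patient must already have left the study; under 7.7 the patient may stay in it. Three things follow.

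1. **Disposition.** The same course of events can be recorded as a discontinuation from Period 4 or as continued participation and completion.
2. **Adverse event collection.** Coding the patient as out of the study may bring the release in 9.2.1 into play while Visits 801 and 802 are still due.
3. **Reading the Period 4 safety tables.** Follow-up emergent events are defined by timing alone. Where 7.7 is followed, events that begin on a new biologic sit in the same rows as events that begin off all treatment, under the earlier study regimen.

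**Working it through.** No figure in the plan bears directly on this point, so the check is a comparison of passages followed by one small calculation.

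**Step 1. Do the rules overlap?**

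| | Protocol 8.2 | Protocol 7.7 |
|---|---|---|
| Trigger | Need for another agent effective in the indication | Use of an axSpA agent excluded during treatment |
| Period | None stated | Period 4, after stopping study treatment |
| Condition | None | Investigator judgement and sponsor medical approval |
| Result | Leaves the study before the agent starts | May take the agent while in Period 4 |

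The Synopsis counts Period 4 as one of the four periods of study participation. Protocol 8.1 records discontinuation from treatment and discontinuation from the study as separate events with separate dates, so 8.2 cannot simply be read as meaning the end of study treatment. The rules overlap and give different results.

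**Step 2. Does safety follow-up differ?** Not as to the visits. The last sentence of 8.2, footnote w and the design-figure footnote all keep Visits 801 and 802. However, 8.2 directs follow-up to Section 9.2, and 9.2.1 ends active seeking of events once the disposition form is complete. The documents do not say whether that form is completed when the patient is coded out under 8.2 or after Visit 802. That is the remaining ambiguity.

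**Step 3. Does efficacy differ?**
- Week 16: a patient who stops study treatment before Week 16 is a nonresponder under Protocol 10.3.4.1 and SAP 6.3.1, whatever the study status.
- Week 52: a patient in Period 4 has either completed Week 52 or already stopped treatment, so the Week 52 status is the same under both rules.
- The Schedule of Activities lists no efficacy scales at Visits 801 and 802, so neither rule adds or removes efficacy data.

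**Step 4. Can the planned tables separate events after a new agent?** SAP 6.11.2 and 6.11.3 define follow-up emergent events as those arising or worsening after Week 52 or the early termination visit. SAP 6.8.2 summarizes concomitant therapy for Periods 2 and 3 only. The tables therefore cannot separate them. The data can: concomitant medications are collected at Visits 801 and 802, and 7.7 requires start and stop dates.

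**Step 5. Size for disposition.** Inputs: about 140 randomized (Protocol 5.2). Assumption: nearly all enter Period 4, as footnote w implies for treated patients. Each patient coded differently moves the Period 4 completion percentage by 1/140 = 0.7 points. The number affected is not in the documents; as a range, 3 patients give 3/140 = 2.1 points and 7 give 7/140 = 5.0 points.

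**The case against.** The strongest reply is that the conflict is mostly about coding. Use of a new agent under 7.7 needs central sponsor approval, which limits how far sites can diverge. The safety visits are required either way. Period 4 analyses are descriptive, with no comparison between groups. Follow-up emergent is a timing label and does not attribute an event to ixekizumab, and one of the Period 4 groups is placebo. All adverse events are listed by patient, so a reader could match events to medication dates by hand. All of this stands and limits the point. It does not remove the clash between 8.2 and 7.7, settle the disposition code, or make the summary tables informative on events after a new agent.

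A reader might also infer something stronger about NSAIDs. Protocol 3.2 says "Though NSAIDs are the first line of drug treatment for axSpA", and 8.2 has no exception for them. Taken literally, a patient who starts an NSAID in Period 3 would be withdrawn and become a Week 52 nonresponder. The documents do not support that reading. Section 7.7 expressly permits NSAID introduction after Week 16, and NSAID intake is itself an endpoint followed through Week 52, which presupposes that these patients stay. What is missing is exception wording in 8.2.

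**Conclusion.** The conflict between Protocol 8.2 and 7.7 for Period 4 is real and should be corrected. Its effect is on Period 4 disposition, at about 0.7 points per patient if nearly all 140 enter that period, and on how clearly the Period 4 safety tables can be read. There is also a smaller ambiguity about active event seeking through 9.2.1.

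Two larger inferences do not hold. The first is that up to 12 weeks of safety follow-up is lost for each affected patient; three separate places in the protocol keep Visits 801 and 802. The second is that Week 52 response rates shift. Assuming that 5% to 20% of patients start an NSAID and that 60% of them would respond gives 0.05 × 0.60 = 3 points to 0.20 × 0.60 = 12 points, but none of these inputs is in the documents and the NSAID reading behind them fails. The Week 16 primary and major secondary tests are untouched.

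The conclusion assumes that some patients start a new axSpA agent in Period 4; the documents give no expected number.

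**What to change.** **Protocol.** Reconcile 8.2, 7.7 and 9.2.1. State which agents, in which period, lead to discontinuation from the study, and add to 8.2 the exception wording for concomitant therapy that 7.7 already permits. The choice of clinical rule is the sponsor's. State also that the adverse event collection already required to Visit 802 applies in either case, and when the disposition form is to be completed for such a patient.

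**SAP.** In the Period 4 tables, flag follow-up emergent adverse events and follow-up emergent serious adverse events by onset before or after the first dose of a new systemic axSpA therapy, using the medication dates already recorded.

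**Cost.** A wording change and one derived flag, with no new data. The downside is sparse cells in a descriptive table.
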